8.1 Site monitoring

Before study initiation, at a site initiation visit or at an investigator’s meeting, a Novartis representative will review the protocol and CRFs with the investigators and their staff. During the study, Novartis employs several methods of ensuring protocol and Good Clinical Practice (GCP) compliance and the quality/integrity of the sites’ data. The field monitor will visit the site to check the completeness of patient records, the accuracy of entries on the eCRFs, the adherence to the protocol and to Good Clinical Practice, the progress of enrollment, and to ensure that study treatment is being stored, dispensed, and accounted for according to specifications. Key study personnel must be available to assist the field monitor during these visits. Continuous remote monitoring of each site’s data may be performed by a centralized Novartis CRA organization. This central analytics organization may also analyze data and identify risks and trends for site operational parameters, and provide reports to Novartis Clinical Teams to assist with trial oversight.

The investigator must maintain source documents for each patient in the study, consisting of case and visit notes (hospital or clinic medical records) containing demographic and medical information, laboratory data, electrocardiograms, and the results of any other tests or assessments. All information on eCRFs must be traceable to these source documents in the patient's file. The investigator must also keep the original informed consent form signed by the patient (a signed copy is given to the patient).

The investigator must give the monitor access to all relevant source documents to confirm their consistency with the eCRF entries. Novartis monitoring standards require full verification for the presence of informed consent, adherence to the inclusion/exclusion criteria, documentation

of SAEs, and of data that will be used for all primary variables. Additional checks of the consistency of the source data with the CRFs are performed according to the study-specific monitoring plan. No information in source documents about the identity of the patients will be disclosed.

8.2 Data collection

Designated investigator staff will enter the data required by the protocol into the EDC system. Designated investigator site staff will not be given access to the system until they have been trained.

Automatic validation procedures within the system check for data discrepancies during and after data entry and, by generating appropriate error messages, allow the data to be confirmed or corrected online by the designated investigator site staff. The Investigator must certify that the data entered into the eCRFs are complete and accurate. After database lock, the investigator will receive copies of the patient data for archiving at the investigational site.

8.3 Database management and quality control

Novartis staff [or CRO working on behalf of Novartis] review the data entered into the CRFs by investigational staff for completeness and accuracy and instruct the site personnel to make any required corrections or additions. Queries are sent to the investigational site using an electronic data query. Designated investigator site staff is required to respond to the query and confirm or correct the data.

Prior/concomitant medications and procedures as well as significant non-drug therapies entered into the database will be coded using the WHO Drug Reference List, which employs the Anatomical Therapeutic Chemical (ATC) classification system. Medical history/current medical conditions and medical history possibly contributing to liver dysfunction as well as adverse events will be coded using the Medical dictionary for regulatory activities (MedDRA) terminology.

Laboratory samples will be processed centrally in Germany and the results will be sent electronically to Novartis (or a designated CRO in Germany).

ECG readings will be processed centrally and the results will be sent electronically to Novartis (or a designated CRO).

Diary data will be entered into an electronic diary by the patient. The system will be supplied by a vendor(s), who will also manage the database. The database will be sent electronically to Novartis personnel (or designated CRO).

Randomization codes and data about all study drug(s) dispensed to the patient and all dosage changes will be tracked using an Interactive Response Technology (IRT). The system will be supplied by a vendor, who will also manage the database. The database will be sent electronically to Novartis (or a designated CRO).

Each occurrence of a code break via IRT will be reported to the clinical team and monitor. The code break functionality will remain available until study shut down or upon request of Novartis.

The occurrence of relevant protocol deviations will be determined. After these actions have been completed and the database has been declared to be complete and accurate, it will be locked and the treatment codes will be unblinded and made available for data analysis.

8.4 Data Monitoring Committee

Not required.

8.5 Adjudication Committee

Not required.

9 Data analysis

The first analysis will be conducted on all patient data when the double-blind treatment epoch of the trial ends. The data will be analyzed by Novartis and/or by the designated CRO.

Analysis sets

The Randomized Analysis Set (RAS) will consist of all participants who received a randomization number, regardless of receiving study medication.

The Full analysis set (FAS) will consist of all participants who received at least one dose of double-blind study medication. In FAS, subjects will be analyzed according to randomized treatment, regardless of the actual treatment received.

The Safety analysis set (SAF) will consist of all randomized subjects who received at least one dose of investigational product and will be analyzed based on actual treatment received.

9.1 Patient demographics and other baseline characteristics

Demographic variables and other baseline characteristics including previous migraine treatments will be summarized. Descriptive statistics (mean, median, standard deviation, minimum, and maximum) will be presented for continuous variables for each treatment group and for all participants (total). The number and percentage of participants in each category will be presented for categorical variables for each treatment group and all participants (total).

In addition, all relevant medical history will be summarized following the same strategy. Any condition entered as medical history or current medical conditions at baseline will be coded using the MedDRA dictionary. Medical history will be summarized by system organ class and preferred term in the MedDRA dictionary. Summaries for migraine specific medical history will be provided as well.

9.2 Treatments

The analysis of study treatment data will be based on the safety set. A data listing and a summary of the investigational drug injections and pill counts (erenumab or topiramate) administered will be provided. Dose levels achieved and no. /percentage of patients titration per visit will be presented for topiramate or matching placebo. The duration of exposure to study treatment will be summarized by treatment group. In addition, the number and percentage of participants receiving rescue medications, concomitant medications, and significant non-drug therapy will be summarized by preferred term (coded by WHO Anatomic Therapeutic Chemical classification [ATC]) and by treatment arm, and be listed.

9.3 Analysis of the primary variable(s)

9.3.1 Variable(s)

The analysis of the primary variable will be based on the following estimand:

- Population – Safety Analysis Set (SAF)
- Variable of Interest: The primary endpoint is the rate of patients discontinuing the allocated study treatment due to an adverse event (AE) during the double-blind treatment epoch.
- Intervention effect – effect between erenumab versus topiramate during double-blind treatment regardless of adherence to randomized treatment.
- Summary measure – odds ratio

9.3.2 Statistical model, hypothesis, and method of analysis.

The null hypothesis to be rejected is that the odds of AE-related treatment discontinuations are equal in both treatment groups. The corresponding alternative hypothesis is that the odds are not equal under erenumab compared to topiramate.

Let p_j denote the proportion of AE-related treatment discontinuations for treatment group j , $j=0, 1$, where

- 0 corresponds to erenumab
- 1 corresponds to topiramate

The following hypotheses will be tested:

$H_0: (p_1 / (1 - p_1)) / (p_0 / (1 - p_0)) = 1$ versus $H_A: (p_1 / (1 - p_1)) / (p_0 / (1 - p_0)) \neq 1$ In other words:

H_0 : The odds ratio of AE-related treatment discontinuations for erenumab vs topiramate is equal to 1, meaning no difference on AE-related treatment discontinuations between the two treatments. H_A : The odds ratio of AE-related treatment discontinuations for erenumab vs topiramate is different from 1.

The primary analysis will be performed comparing treatments with respect to the primary efficacy variable in a logistic regression model with the factors treatment and stratification factor (migraine days during the baseline epoch). The odds ratio and its 95% confidence interval

(CI) and p-value will be given. The null hypothesis of equal odds will be rejected if the 2-sided p-value from the logistic regression model for the factor “treatment” is <0.05 ; however, superiority of erenumab will be claimed only if the direction is correct, i.e. if the odds of response are lower under erenumab compared to topiramate.

9.3.3 Handling of missing values/censoring/discontinuations

For every patient, it can be determined whether he/she discontinued for AE-related reasons. Non-AE-related discontinuations or losses to follow up will not be counted as AE-related discontinuations. AE-related discontinuations are counted as events, discontinuation due to other reasons are not counted as events.

[REDACTED]

9.4 Analysis of secondary variables

The secondary variable is the achievement of at least a 50% reduction from baseline in monthly migraine days (MMD) over the last 3 months (months 4, 5, and 6) of the double-blind treatment period.

The analysis of the primary variable will be based on the following estimand:

- Population – Full Analysis Set (FAS)
- Variable of Interest: number of patients with at least 50% reduction from baseline in monthly migraine days (MMD)
- Intercurrent event: discontinuation of study medication – effect between erenumab versus topiramate assuming to evaluate treatment policy
- Intercurrent event: discontinuation of study or lost to follow up – effect between erenumab versus topiramate assuming no response could be achieved
- Summary measure – odds ratio

All the subjects’ data collected regarding 50% response of MMD will be used in the analysis regardless whether subjects complete the study drug or not. Subjects with missing response information on this endpoint will be imputed as non-response (non-responder imputation). A logistic regression model including treatment group, baseline value, and stratification factor will be used to perform the treatment comparison (erenumab vs. topiramate) at end of the DBTE. Additional to the odds ratio obtained from the logistic regression, estimates for the risk ratio and the risk difference (with corresponding confidence intervals and p-values) will be calculated for the secondary endpoint.

9.5 Analysis of exploratory variables

Exploratory variables are the patient reported outcomes (PROs) HIT-6 and SF-36 [REDACTED]. The analysis of PROs [REDACTED] will be described in detail in the statistical analysis plan (SAP).

9.5.1 Safety variables

9.5.1.1 Adverse events

Treatment emergent adverse events (events started after the first dose of study treatment or events present prior to the first dose of study treatment but increased in severity based on preferred term) will be summarized.

Adverse events will be summarized by presenting, for each treatment group, the number and percentage of patients having any AE, having an AE in each primary system organ class and having each individual AE (preferred term). Summaries will also be presented for AEs by severity and for study treatment related AEs. If a patient reported more than one adverse event with the same preferred term, the adverse event with the greatest severity will be presented. If a patient reported more than one adverse event within the same primary system organ class, the patient will be counted only once with the greatest severity at the system organ class level, where applicable. Serious adverse events will also be summarized.

Separate summaries will be provided for death, serious adverse event, other significant adverse events leading to discontinuation and adverse events leading to dose adjustment (including study treatment discontinuation).

9.5.1.2 Laboratory data

The summary of laboratory evaluations will be presented for three groups of laboratory tests (hematology, serum chemistry and urinalysis). Descriptive summary statistics for the change from Baseline to each study visit will be presented.

These descriptive summaries will be presented by test group, laboratory test and treatment group. Change from Baseline will only be summarized for patients with both Baseline and Post-Baseline assessments.

For each parameter, the maximum change from Baseline within each study period will be analyzed analogously.

9.5.1.3 Vital signs

Analysis of the vital sign measurements using summary statistics for the change from Baseline for each Post-Baseline visit will be performed. These descriptive summaries will be presented by vital sign and treatment group. Change from Baseline will only be summarized for patients with both Baseline and Post-Baseline values.

9.5.2 Resource utilization

9.5.3 Not applicable. PK/PD

Not applicable.

9.5.4 DNA

Not applicable.

9.5.5 Blood Biomarkers

Not applicable.

9.6 Interim analyses

Not applicable.

[REDACTED]

10 Ethical considerations

10.1 Regulatory and ethical compliance

This clinical study was designed and shall be implemented, executed and reported in accordance with the ICH Harmonized Tripartite Guidelines for Good Clinical Practice, with applicable local regulations (including European Directive 2001/20/EC, US CFR 21, and Japanese Ministry of Health, Labor, and Welfare), and with the ethical principles laid down in the Declaration of Helsinki.

10.2 Informed consent procedures

Eligible patients may only be included in the study after providing written (witnessed, where required by law or regulation) IRB/IEC-approved informed consent. The patient is capable of doing so, he/she must indicate assent by personally signing and dating the written informed consent document or a separate assent form. Informed consent must be obtained before

conducting any study-specific procedures (e.g. all of the procedures described in the protocol). The process of obtaining informed consent must be documented in the patient source documents.

Novartis will provide a proposed informed consent form to investigators that complies with the ICH GCP guideline and regulatory requirements and is considered appropriate for this study.

Women of child bearing potential must be informed that taking the study treatment may involve unknown risks to the fetus if pregnancy were to occur during the study and agree that in order to participate in the study they must adhere to the contraception requirement for the duration of the study. If there is any question that the patient will not reliably comply, they must not be entered in the study.

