 14. Myocardial infarction, stroke, transient ischemic attack, unstable angina, or coronary artery bypass surgery or other revascularization procedures within 12 months prior to screening
 15. History or current diagnosis of ECG abnormalities indicating significant risk of safety for patients participating in the study
 16. History of malignancy of any organ system (other than localized basal cell carcinoma of the skin or *in situ* cervical cancer), treated or untreated, within the past 5 years, regardless of whether there is evidence of local recurrence or metastases
 17. Hepatic disease by history or total bilirubin $\geq 2 \times \text{ULN}$ or ALT or AST $\geq 3 \times \text{ULN}$ as assessed by central laboratory at initial screening
 18. Pregnant or nursing (lactating) women
 19. Women of child-bearing potential, defined as all women physiologically capable of becoming pregnant, unless they are using highly effective methods of contraception during dosing and for 110 days after stopping of study medication. Highly effective contraception methods include:
 - Total abstinence (when this is in line with the preferred and usual lifestyle of the patient). Periodic abstinence (e.g., calendar, ovulation, symptothermal, post-ovulation methods) and withdrawal are not acceptable methods of contraception
 - Female sterilization (have had surgical bilateral oophorectomy with or without hysterectomy) total hysterectomy or tubal ligation at least 6 weeks before taking investigational drug. In case of oophorectomy alone, only when the reproductive status of the woman has been confirmed by follow up hormone level assessment

- Male sterilization (at least 6 months prior to screening). For female patients on the study, the vasectomized male partner should be the sole partner for that patient and should have received medical assessment of surgical success.
- Use of oral, (estrogen and progesterone), injected or implanted hormonal methods of contraception or placement of an intrauterine device (IUD) or intrauterine system (IUS) or other forms of hormonal contraception that have comparable efficacy (failure rate <1%), e.g. hormone vaginal ring or transdermal hormone contraception
- In case of use of oral contraception women should have been stable on the same pill for a minimum of 3 months before taking investigational drug

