5.5.4 Instructions for prescribing and taking study treatment

The investigational product dose is either 70 mg or 140 mg depending on the investigators decision, which has to be made for each patient individually and in accordance with the product information: the recommended dose is 70 mg, some patients may benefit from 140 mg (see Section 5.1 of AIMOVIG® SmpC).

In case of insufficient response, the dose may be escalated from 70 mg to 140 mg. Possible reasons for up titration could be, but are not limited to:

- insufficient response as deemed by physician and/or patient
- reduction of acute medication use not satisfactory
- insufficient improvement in life quality

An adjustment of the 70 mg dose to 140 mg can be performed at any time during the DBTE. The investigational product dose of 140 mg must not be changed once a patient received the dose during DBTE.

Reference treatment doses are determined during the uptitration phase and must aim to reach the recommended daily treatment dose of 100 mg topiramate in accordance to the German SmPC. The reference treatment dose established during the up titration phase must not be changed during the 18-week maintenance phase.

There are no temporal restrictions for the investigational or the reference treatment (e.g., proximity to meals, sleep or activity).

Test-IMP:

70 mg and 140 mg erenumab or respective placebos will be administered by qualified study staff at each dosing visit during the 24 week double-blind treatment epoch (i.e., at Day 1 and Week 4, Week 8, Week 12, Week 16 and Week 20). Subcutaneous (s.c.) injections are to be given for each investigational product administration. For purposes of study treatment dosing, “q.m.” refers to an every 4 weeks injection regimen. The study drug administration date should be in 4 week increments (+/- 4 days) from the first dose of study drug. Any dose administrations that may occur greater than +/- 4 days from the 4 week time point (e.g., patient unavailability) should be discussed with the Sponsor prior to dosing. The anatomical sites for administration of investigational product are the upper arm, upper thigh, or abdomen; the location of the injection site should be documented in the source document. In order to reduce irritation at the injection site, the investigational product should be stored at room temperature for 30 minutes prior to the administration.

Control-IMP:

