Patients who are not able to tolerate 50 mg have to be discontinued from drug, but should remain in the trial for documentation purposes. During this time, patients may use treatments described under 5.5.6 for their acute migraine attacks.

Maintenance phase (start of week 7 to end of week 24):

Control-IMP doses are determined during the uptitration phase and must not be changed during the 18-week maintenance phase. Patients have to remain on their highest tolerated dose (50 mg, 75 mg or 100 mg topiramate) throughout maintenance phase. If a patient cannot tolerate dose during maintenance phase, he/she has to be discontinued from all study treatment, but should remain in the trial. This patient is allowed to continue using rescue medication as described under 5.5.6.

All kits of study treatment assigned will be recorded in the IRT. Novartis monitors will reconcile treatment assigned vs treatment administered and ensure that the information is congruent during their monitoring visits.

Tapering off

Control-IMP should be tapered off by patients who complete the study (Visit 199, end of week 24) or discontinue study treatment after receiving a daily dose of 75 mg or 100 mg Control-IMP. Tapering off is performed by reducing the daily dose of Control-IMP by 50 mg for one week before a patient stops taking the drug.

Exemplatory Tapering off scheme:

Patient on 100 mg/day topiramate --> One week 50 mg/day topiramate --> No more medication

Patient on 75 mg/day topiramate --> One week 25 mg/day topiramate --> No more medication

Patient on 50 mg/day topiramate --> No more medication (no tapering off required)

Patient on 25 mg/day topiramate --> No more medication (no tapering off required)

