5.6.5 Early study termination by the sponsor

The study can be terminated by Novartis at any time for any reason. This may include reasons related to the benefit-risk assessment of participating in the study, practical reasons, or for regulatory or medical reasons (including slow enrollment). Should this be necessary, the patient must be seen as soon as possible and treated as a prematurely withdrawn patient. The investigator may be informed of additional procedures to be followed in order to ensure that adequate consideration is given to the protection of the patient's interests. The investigator will be responsible for informing the Institutional Review Board / Independent Ethics Committee (IRBs/IECs) of the early termination of the trial.

6 Visit schedule and assessments

Table 6-1 and Table 6-2 list all of the assessments and indicate with an "X" when the visits are performed.

Patients must be seen for all visits on the designated day, or as close to it as possible. Missed or rescheduled visits should not lead to automatic discontinuation.

During visits 102 to visit 107, intervals between visits must not exceed 7 +/- 1 day calculated from Visit 101 (Day1), to ensure continuous supply regarding oral medication.

During visits 108 to visit 199, intervals between visits should not exceed 28 +/- 4 days calculated from Visit 101 (Day 1). If the visit has to be scheduled outside this window, an approval from the sponsor has to be collected to ensure continuous supply of oral medication and patient safety regarding s.c. medication.

	Screen	Baseline	Double – Blind Treatment Epoch (Titration)						Double – Blind Treatment Epoch (Maintenance)						Follow Up ²
Visit number ¹	0	1	101	102	103	104	105	106	107	108	109	110	111	199	201
End of Week	-6	-4	0	1	2	3	4	5	6	8	12	16	20	24	28
Day	-42	-28	1	8	15	22	29	36	43	57	85	113	141	169	197
Baseline Phase Completion form		x													
Double-Blind Treatment Phase Completion form														x	
Follow-Up Phase Completion form															x

- 1 – All study visit target dates are to be calculated from the Day 1 visit date and all study procedures for a given visit should be completed on the same day.
- 2 – The Follow-Up Visit is required 8 weeks after last IMP injection (erenumab / corresponding Placebo) for patients who discontinue the study or 4 weeks after V199 for patients who complete the study. The Follow-Up visit can be skipped if any other safety follow up visit occurred 8 weeks after last IMP injection.

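### The consent section (10.2) ends the contraception agreement and the fetal-risk warning with the study, but exclusion 19 runs 110 days past stopping study medication; on target days a completer's last visit comes 54 days too early, counted from the last injection

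*Protocol*

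**What the plan says.** Protocol Section 4.2, exclusion criterion 19, excludes women of childbearing potential unless they are "using highly effective methods of contraception during dosing and for 110 days after stopping of study medication".

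Protocol Section 10.2 covers the same subject at consent. Women are to be told that study treatment "may involve unknown risks to the fetus if pregnancy were to occur during the study", and to agree that "they must adhere to the contraception requirement for the duration of the study". The section adds: "If there is any question that the patient will not reliably comply, they must not be entered in the study". It mentions neither the 110 days nor criterion 19.

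For the end of a patient's participation, Table 6-1 footnote 2 places the follow-up visit V201 "4 weeks after V199 for patients who complete the study". The table gives V201 a target of Day 197, and Section 5.6.1 describes the same visit as 8 weeks after the last injection. The SAP (Section 2.1.1.1) defines a patient's end of study as the last date on which she took part.

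**The concern.** The two sections give different end points for one safety instruction, and the shorter one stands in the section that guides the consent discussion. If that discussion follows the wording of 10.2, a woman could take both the contraception requirement and the fetal risk to end at her last visit. No scheduled visit comes after V201 to correct this. Protocol Section 3.6 says that CGRP may have an important role in fetoplacental development and fetal survival. Under Section 5.4 patients stay blinded until the primary analysis, so a woman cannot simply assume that she was not on erenumab.

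A likely origin, offered only as inference, is the cut in safety follow-up from 12 to 4 weeks in Amendment 1. With 12 weeks, the last visit would have fallen on Day 169 + 84 = 253, which is 112 days after the last injection, so the duration of the study would have covered 110 days from that injection. The point rests on the current text, not on the amendment log.

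**Working it through.** **Inputs (Protocol)**

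- Last injection: Week 20 (Section 5.5.4), target Day 141 (Table 6-1).
- V199: Day 169. V201: Day 197 (Table 6-1).
- Contraception period: 110 days after stopping (exclusion 19).
- Injection window: "The study drug administration date should be in 4 week increments (+/- 4 days) from the first dose of study drug". Section 6 gives V199 the same 4 days either way. No window is stated for V201.
- Tablets run to Week 24. Patients on 75 or 100 mg then taper for one week (Section 5.5.4).

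**Reproducing the plan's own intervals.** 197 − 141 = 56 days = 8 weeks after the last injection. 197 − 169 = 28 days = 4 weeks after V199. Both agree with the text.

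**Gap for a completer.** Gap = (day of stopping + 110) − day of V201. On target days, from the last injection: 141 + 110 = 251, and 251 − 197 = **54 days**.

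**Windows.** The injection falls on Day 137 to 145 and V199 on Day 165 to 173. Table 6-1 supports two readings of V201. Footnote 2 sets it 28 days after V199, which gives Day 193 to 201. Footnote 1 counts all visit targets from Day 1, which fixes it at Day 197.

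- V201 set from the actual V199: minimum 137 + 110 − 201 = 46; maximum 145 + 110 − 193 = 62.
- V201 fixed at Day 197: minimum 137 + 110 − 197 = 50; maximum 145 + 110 − 197 = 58.

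**If study medication includes the tablets.** The glossary counts topiramate as study treatment, and Section 5.5.4 places the taper "for one week before a patient stops taking the drug", which supports a later start of the 110 days.

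| Count starts at | 110 days end | Gap on target days | V201 = actual V199 + 28 | V201 fixed at Day 197 |
|---|---|---|---|---|
| Last injection, Day 141 | Day 251 | 54 | 46 to 62 | 50 to 58 |
| Last tablet at V199, Day 169 | Day 279 | 82 | 82 (110 − 28) | 78 to 86 |
| End of taper, Day 176 | Day 286 | 89 | 89 (7 + 110 − 28) | 85 to 93 |

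If the last tablet is taken on the day before V199, the target-day figures fall by one, to 81 and 88. In round terms the tablet and taper counts give about 80 to 90 days.

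**Other patients**

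- Leaves the study and returns about 8 weeks after the last dose (Section 5.6.2): 110 − 56 = 54 days.
- Stops treatment but stays on the abbreviated schedule to Day 197: no gap if the last dose was on or before Day 197 − 110 = 87. If it was on Day 113, the gap is 113 + 110 − 197 = 26 days.

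**Could Section 7.1 cover the gap?** It still puts the end-of-study visit 16 weeks after the last injection: 141 + 112 = Day 253. That would pass the injection count by 253 − 251 = 2 days, but fall short of the tablet count by 279 − 253 = 26 days and of the taper count by 286 − 253 = 33 days. It also contradicts the 8 weeks in Section 5.6.1, Table 6-1 (footnotes 2 and 8) and Section 7.2.2, so it cannot be relied on.

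**The case against.** The strongest reply is that 10.2 sets no rule of its own. It speaks of the contraception requirement as something already defined, and the only such requirement with methods and a duration is exclusion 19. A woman who meets exclusion 19 also meets 10.2, so no site has to break one section to follow the other. Eligibility must be confirmed before randomization (Section 5.3), and adherence to the criteria is fully source-verified (Section 8.1). A woman who may not reliably comply is not to be entered. Patients are informed through a consent form that the ethics committee approves, and that form may well state the 110 days.

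Much of this stands. A reader might infer that the protocol lacks post-treatment contraception cover, or that women were told a shorter period. The documents support neither: exclusion 19 is in force, and the consent form was not available. Nor should one infer that later pregnancies go unreported, since Section 7.5 sets no end date for reporting. It would also be wrong to present 82 and 89 days as fixed, because they vary if V201 is tied to Day 1.

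What does not stand is that the wording is harmless shorthand. Even if the requirement means exclusion 19, 10.2 attaches its own, shorter end point to it, and the fetal-risk statement does not refer to the criterion at all. Reading the study as the whole trial up to the last patient's last visit (Section 3.1) would still leave the last women enrolled uncovered.

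**Conclusion.** The point holds as an inconsistent and too-short end point in the consent section. For a completer the shortfall is 54 days on target days, counted from the last injection. It is 46 to 62 or 50 to 58 days with the windows, depending on how V201 is set, and about 80 to 90 days if study medication includes the tablets or the taper. No count removes it for a completer.

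This rests on three assumptions: the study means the woman's own participation; the injection and V199 stay within their stated windows; and V201 falls either exactly 28 days after the actual V199 or on Day 197. Exclusion 19 does not say whether the 110 days run from the injection or the last tablet, so the longer figures are interpretation; the 54 days are enough to make the point. Any effect on patients depends on the unseen consent form.

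**What to change.** In Section 10.2, replace the study-duration end point of the contraception agreement with the period in exclusion criterion 19, namely dosing plus 110 days after study medication is stopped, and cite the criterion. Extend the fetal-risk statement in the same sentence to that period. Check that the consent form states it. Do not lean on the 16 weeks in Section 7.1 to close the gap.

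The cost is one sentence and a check of the consent form. No visits, tests, data collection or analyses are added.
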